11.4. Visits 10-15/Days 8-13

- Update any changes in medical history or concomitant medications and non-drug therapies.
- Assess for adverse events since last visit.
- Each bandage will be removed and replaced with a new bandage, one test site at a time.
- Written and verbal instructions will be provided.
- Subjects will be informed of their next appointment.

11.5. Final Visit 16/Day 14

- Update any changes in medical history or concomitant medications and non-drug therapies
- Assess for adverse events since last visit
- Subjects will acclimate in the test facility for at least 15 minutes in a temperature controlled setting of 68-75°F
- Bandages will be removed prior to assessments.
- Wound assessments outlined at visit 2 will also be completed at this visit in the order listed below:
 - [REDACTED]
 - Trans Epidermal Water Loss (TEWL; tewameter): Noninvasively measures water evaporation from the skin, which is a measure of skin barrier function. These measurements will be done three times for each test site.
 - [REDACTED]

- Diffuse Reflectance Spectroscopy (DRS): Noninvasively measures redness by oxy-, deoxy-hemoglobin, and melanin levels in the skin. Five repetitive spectra acquisition will be implemented for each test site.
- Microbiome [REDACTED] sampling: Swabs will be used to collect bacteria [REDACTED] from the skin surface. A total of 2 swabs will be taken per site, plus control swabs.
- Subject Disposition

11.6. Randomization

Subjects who meet the eligibility criteria, will be randomized during Visit 2. The Sponsor will be responsible for the generation of the randomization schedule and products will be packaged according to this randomization schedule.

11.7. Unscheduled/ Follow-up Visit

Subjects may be scheduled for a follow-up visit, as determined to be necessary by the Investigator. The Investigator will provide any applicable post-study wound care treatment as needed. All follow-up information will be documented as applicable.

If a subject experiences an adverse event that is deemed to have a causal relationship to the trial procedures, when the subject either completes or discontinues participation in the study, he/she must return to the site for a follow-up visit until the event is stabilized at a level acceptable to the Investigator.

11.8. Procedures for Tape-stripping, Bandage Application and Bandage Removal

See appendix 1 for diagram for test site numbers.

11.8.1. Site Selection

Six test sites will be identified by the investigative staff and numbered from 1 to 6. The selected sites will be free from nevi or other skin conditions. Using a template and permanent marker, six (6) test areas will be marked at least 2" – 3" apart from each other

on the back on each subject. Test sites will be positioned side by side on a rectangular design so that three are made on each side of the spine. The test sites will be located paraspinally with three test sites on each side of the mid back below the shoulder blades.. Enough space will be left between the test sites so that the bandages can be placed over the wounds without an overlap. If the subject is female, the test sites will be positioned below the bra line.

The randomization schedule will detail the treatment assignments for each test site. Tape Stripping Procedure & Preparation

- The subjects will rest in a prone position (front or ventral surface downward) for the wounding procedure. Instruments used will be sterile. The Investigator or trained clinician creating the wounds as well as assisting staff will wear gloves. Test sites may be re-marked as needed.
- All test sites will be cleaned with an alcohol wipe prior to wounding. NOTE: the test site randomly assigned to be intact (unwounded) and untreated will not be wiped with alcohol.
- Superficial irritation will be created by a tape stripping method to obtain a glistening layer using 3M tape or similar ,(3M St. Paul, MN, USA) for sequential stripping of the epidermis of the test site.
- Strips may be pre-cut and placed on release paper.
- Approximately a 1 cm x 1 cm wound will be created on each of the designated test sites.
- The technician will place the tape on the test site, press it down, rub firmly within the test site marks, and remove the strip with a strong and quick stroke.
- This process will be repeated until a clear glistening layer will be visualized upon removal of the strip. The number of stripplings necessary to reach the glistening layer varies among subjects and depends upon the thickness and looseness of the subject's stratum corneum layer.
- The number of strips used per site will be recorded in the source document.

11.8.2. Bandage Application and Removal

Trained personnel will apply/re-apply the bandages to the subjects according to the randomization schedule. Subjects will be placed in a seated or prone position during the bandage application process.

All staff applying test products will wear gloves. Test products will not be applied if wounds show signs of infection, excessive redness, pain, or swelling. Each individual test product is for a single use and will not be reused. Each product will be placed on the designated test site, ensuring that the pad stock covers the wound, adhesive tabs should not directly contact the wound. To prevent tape irritation to the surrounding skin, trained personnel will rotate the bandages in a wheel-like fashion with each application so that

adhesive is not continuously applied to the same area of skin, while also ensuring that the padstock covers the wound completely. Reinforcement tape may be applied to each bandage (covering only the adhesive portions of the bandage, not the central portion containing the pad) to ensure that bandages will remain in place until the next visit, only as needed. Subjects will also be provided a roll of tape to take home for use in case bandages become loose between clinic visits.

Only trained personnel will remove and replace bandages during scheduled visits by gently lifting one corner of the bandage with upward force until one side is completely detached. The other side will be removed in the same manner. Bandages will be removed preserving the intact wound condition as best as possible. All used bandages and tapes will be discarded in a biohazard water container.

If a bandage falls off at home, subjects will be instructed to report the date and time that the bandage fell off and report that information at their next visit. Bandages will not be replaced at home if they fall off. Subjects will be instructed to retain any bandages that have fallen off and bring them to their next appointment.

11.9. Subject Acclimation

Subjects will acclimate in the test facility for at least 15 minutes in a temperature controlled setting of 68-75°F prior to assessments and swabbing. All bioinstrument assessments and swabbing will be completed in a temperature controlled setting of 68-75 F and 35-65 Relative Humidity. Temperature and humidity from the assessment area will be recorded daily during study visits.

11.10. Life Style Guidelines

Subjects will be requested not to immerse the bandages in water (i.e. no baths, swimming, hot tubs, etc.). Subjects will only be allowed to shower during the study using the provided [REDACTED] WASH. Subjects will be instructed to shower the night prior to their clinic visits to allow the bandages sufficient time to dry prior to removal/evaluations. Subjects should not apply lotions, creams, perfumes, or other topical products to their back during the study, to keep the back as clean as possible.

11.11. Contraception for females

Female subjects with reproductive potential must agree to practice a medically acceptable form of birth control during the study. Females must have used such birth control for at least 3 months prior to the Screening visit and for 30 days following the last application of investigational product.

Medically acceptable forms of birth control that may be used by the subject and/or his/her partner include:

- Established use of hormonal methods of contraception (oral, injected, implanted, patch or vaginal ring)
- Barrier methods of contraception with spermicide: condom or occlusive cap (diaphragm or cervical/vault caps) with spermicidal foam/gel/ film/ cream/ suppository.
- Intrauterine device (IUD) or intrauterine system (IUS)
- Surgical sterilization (e.g., vasectomy that has been confirmed effective by sperm count check, tubal occlusion, hysterectomy, bilateral salpingectomy)
- Abstinence from heterosexual intercourse: When this is in line with the preferred and usual lifestyle of the subject. Periodic abstinence (e.g., calendar, ovulation, symptothermal, post-ovulation methods) and withdrawal are not acceptable methods of contraception.

A female subject who is postmenopausal (i.e., amenorrheic for at least 12 months prior to the Screening visit) is not considered of reproductive potential.

11.12. Contraception for Males

Male participants will be informed about potential risks of the study medication for embryos and fetuses.

Male subjects are instructed to prevent their partner from becoming pregnant from the first application of investigational product. Information about effective means of birth control (hormonal contraception, intrauterine devices, vasectomy, sexual abstinence) will be provided, and discussed as appropriate with individual subjects.

11.13. Prior and Concomitant Medications

Any medications taken before the first application of investigational product will be defined as a prior medication. Medications taken after the first application of investigational product until after discharge from the study will be defined as concomitant medications.

Female subjects who are using hormonal contraceptives will continue with their prescribed medication. The investigator should approve medication that may be required due to unexpected illness during the study. The usage must be reported to the sponsor and recorded on the case report forms.

Subjects will abstain from using prescription or nonprescription drugs, and dietary/herbal supplements in accordance with the inclusion or exclusion criteria. All concomitant medication taken during the study must be recorded with indication, dose, start and stop times, and dates of administration. All subjects will be questioned about concomitant medication upon admission for each study period.

11.14. Treatment Compliance

The packaging of investigational product will be managed by the Sponsor according to applicable regulatory requirements.

The designated personnel will dispense the investigational product following the procedures set out in the study protocol. The investigator will be responsible for assuring the retrieval of all investigational products from subjects, if the investigational product were to accidentally come off at a location other than the clinical site.

The investigator will maintain accurate and adequate records including dates of receipt and return of investigational product shipments, and quantities received from the Sponsor as well as dates and amounts dispensed. The Investigational Product Accountability Log will be used to record this information.

Compliance of study subjects will be monitored by a visual inspection of the bandages to ensure they are being treated in the appropriate fashion (i.e. the subject is not swimming or using a hot tub, etc.).

11.15. Rescue Therapy

Subjects may be withdrawn from the study at their request or at the discretion of the Investigator if they experience excessive pain, discomfort, signs of infection, or excessive bleeding. In addition, the following therapies may be provided at the discretion of the Investigator: Acetaminophen, topical or systemic antimicrobial therapy, topical lidocaine, and/or pressure or topical aluminum chloride solution in the case of excessive bleeding.

11.16. End-of-Study Procedures

End of study is defined as the subject's last day of study participation due to study completion or early withdrawal/termination. Assessment of adverse events, collection of study materials and subject disposition should be completed.

12. ASSESSMENTS

Study staff will be trained by the sponsor on the use of all equipment, as well as the swabbing procedure. A separate document will detailed step by step instructions for equipment operation and swabbing.

12.1.2. Transepidermal Water Loss

This assessment will be performed by trained study staff at Days 0,1-7, and 14 for each test site.

Transepidermal water loss (TEWL) measurements are performed in many laboratories and discussed in the literature as a method to characterize barrier function of the stratum corneum (SC) [8]. There are various types of instruments which measure TEWL. All instruments contain relative humidity and temperature sensors and measure flux density ($\text{g/m}^2\text{h}$) through the SC. It is a open-chamber instrument which measures water vapor flux through a chamber, calculating TEWL values based on changes in relative humidity of the chamber, with a range of 3-200 $\text{g/m}^2\text{h}$.

Wound Care Microbiome Study
Protocol: CO-170726100607-SACT
Amendment 2: 22JAN2018

TEWL readings will be done in triplicate and each reading will be recorded on the source document.

12.1.5. Diffuse Reflectance Spectroscopy (DRS)

This assessment will be performed by trained study staff at Days 0, 1-7 and 14 for each test site. DRS is a non-invasive diagnostic tool that uses an optical fiber probe to deliver and collect light after multiple scattering and absorption events in the skin. The probe is a bifurcated fiber bundle and one of its legs is used for delivery of light and the other leg is used for collection of light that is remitted from the skin. The distal end of the probe consists of randomized fiber bundle from both legs. Analysis of the reflectance spectrum provides information on skin redness by measuring the levels of skin chromophores such as oxy-hemoglobin, deoxy-hemoglobin, and melanin.

A transparent membrane will be placed over each test site so the probe will not directly contact the skin. Five repetitive spectra acquisition will be implemented for each wound test site for each time point.

For DRS measurements, the site will provide the DRS readings to Sponsor who will derive the DRS measurements. These measurement will be exported into an macro-enabled audit-trail excel workbook and provided to Quantitative Sciences department for analysis.

12.1.6. Skin Microbiome [REDACTED] Sampling

Non-invasive collection of the skin microbiome [REDACTED] is conducted by swabbing a polyester-tipped applicator, that has been wetted by 0.85% saline, across a defined test site for thirty seconds. Two test swabs will be collected from each test site at each time point.

Two control swabs must be collected at the beginning of each day that subjects are sampled.

Collected swabs will be sent to RTL Genomics for microbial DNA extraction, sequencing and analysis. [REDACTED]

The results of the microbiome [REDACTED] sampling will be analyzed and summarized in a report which will be appended to the clinical study report.

12.2. Safety Assessment

At the Screening visit (Visit 1), the Investigator will perform an examination to make sure the subject has generally healthy skin and is eligible to participate in the study. Any skin abnormalities, condition, or exam finding that was present at the time of examining the

subject's back (e.g., tattoos, bruising, mechanical trauma, etc.) which does not exclude the subject and has not worsened during the course of the study will be considered medical history and not captured as an AE in subsequent exams.

Expected reactions (e.g. bleeding, pain, itching, etc.) related to the tape stripping procedure, normal healing process, and adhesive bandage application and removal will not be captured as adverse events unless there is exacerbation of these reactions as judged by Investigator. These reactions will be documented on the case report form. The Investigator is to report all directly observed adverse events and all adverse events spontaneously reported by the study subject. In addition, each study subject will be questioned about adverse events. The Investigator's assessment of causality must be provided for all adverse events.

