14.4. Safety Analysis

All subjects who receive at least one dose of study treatment will be included in the safety analysis. All adverse events reported during the adverse-event reporting period will be listed by subject number and treatment. The number of subjects experiencing adverse events will be presented by body system, preferred term, and treatment. The latest version of the Medical Dictionary for Regulatory Activities (MedDRA) will be used as the adverse event classification system.

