4.3 Safety Assessments and Endpoints

Safety assessments consist of Adverse Events.

- Number and percentage of subjects with treatment-emergent adverse event
- Number and percentage of subjects with treatment-related adverse event
- Number and percentage of subjects with serious adverse event

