4.4 Other Endpoints

Not applicable.

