14.3 Safety

Section / Table No	Title	Population / Analysis Sets
Table 14.3.1	Subjects with Treatment-Emergent Adverse Events by System Organ Class and Preferred Term	Safety Analysis Set
Table 14.3.2	Subjects with Treatment-related Adverse Events by System Organ Class and Preferred Term	Safety Analysis Set
Table 14.3.3	Subjects with Serious Adverse Events by System Organ Class and Preferred Term	Safety Analysis Set

FIGURES:

None .

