APPENDIX 2: DATA LISTINGS

The following listings are planned for subsections in Appendix of Clinical Study Report. The numbering and titles of data listings in this document serve as guidance; the exact numbers and titles may be modified as appropriate.

Listing No.	Title	Population
16.1.7	Randomization Scheme and Codes	All randomized Subjects
16.2.1.1	Subject Disposition Listing	All randomized Subjects
16.2.1.2	Discontinued Subjects	All randomized Subjects
16.2.2	Subjects with Protocol Deviations	All randomized Subjects
16.2.3	Subjects Excluded from the Primary Analysis	All randomized Subjects
16.2.4.1	Demographic and Baseline Characteristics	All randomized Subjects
16.2.6.1	Trans Epidermal Water Loss (TEWL) Measurements	All randomized Subjects
16.2.6.2	[REDACTED] Measurements	All randomized Subjects
16.2.6.3	Skin pH Measurements	All randomized Subjects
16.2.7.1	Subjects with Adverse Events	All randomized Subjects
16.2.7.2	Subjects with Serious Adverse Events	All randomized Subjects
16.2.7.3	Subjects Withdrawn from Investigational Product due to Adverse Events	All randomized Subjects

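### Expected bandage and wound reactions are recorded on the case report form but reach no planned table or listing, and the SAP's adverse event summaries are not split by treatment

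*Protocol*

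**What the plan says.** Protocol 12.2 states that expected reactions "related to the tape stripping procedure, normal healing process, and adhesive bandage application and removal will not be captured as adverse events", with one exception: "unless there is exacerbation of these reactions as judged by Investigator". It gives no grade or threshold for exacerbation. It then adds: "These reactions will be documented on the case report form". Protocol 17.1 equates the case report form with the EDC system and says that EDC holds the data needed for analysis.

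SAP 4.3 opens with "Safety assessments consist of Adverse Events", and SAP 4.4 (other endpoints) is marked not applicable. SAP Appendix 1 plans three safety tables: 14.3.1, titled "Subjects with Treatment-Emergent Adverse Events by System Organ Class and Preferred Term", 14.3.2 for treatment-related events and 14.3.3 for serious events. The safety listings in Appendix 2 run from 16.2.7.1 ("Subjects with Adverse Events") to 16.2.7.3, and all concern adverse events.

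On layout, Protocol 14.4 says: "The number of subjects experiencing adverse events will be presented by body system, preferred term, and treatment". It also lists events by subject and treatment. SAP 6.5 summarises by body system and preferred term only, and lists by subject number only.

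**The concern.** The protocol asks the site to write down a class of reactions, and the analysis plan then does nothing with them. These are the reactions most closely tied to the products. Protocol 12.2 names bandage application and removal as a source, and Protocol 11.8.2 has the bandages rotated to avoid irritation from the adhesive. The four bandages differ in size, and Table 3 describes one as medicated. Each subject carries all four bandages and both controls at randomised sites, so reactions could be set side by side within a subject if the site were known.

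At stake is the completeness of the safety section. A reader of the study report would see adverse event tables without the ordinary local reactions. Under the SAP text, those tables would also not say which bandage an exacerbated reaction belonged to.

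**Working it through.** The plan states no reaction rate, power or effect size, so there is no figure to reproduce. The check has two parts.

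**1. Following the record through the documents**

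| Step | Place | Non-exacerbated expected reactions | Exacerbated reactions |
|---|---|---|---|
| Capture | Protocol 12.2 | Case report form, not adverse events | Adverse events |
| Safety analysis | Protocol 14.4 | Not mentioned | By treatment |
| Endpoints | SAP 4.3, 4.4 | None | Adverse event counts |
| Safety analysis | SAP 6.5 | Not mentioned | No treatment split |
| Tables | SAP 14.3.1–14.3.3 | None | Titles name no treatment or site |
| Listings | SAP 16.2.7.1–16.2.7.3 | None | Adverse event listings |

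The safety tables and listings carry no redaction. The one blacked-out table title (14.2.4) and the one blacked-out listing title (16.2.6.2) both end in Measurement(s) and sit among the instrument readings.

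**2. How much information the exacerbation filter could remove (illustration)**

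Inputs:
- n = 35 randomised (Protocol synopsis).
- True reaction rates p1 and p2 on two bandages: assumed.
- Fraction f of reactions judged exacerbated: assumed.
- Independence between sites within a subject: assumed.
- Adverse events split by site, as Protocol 14.4 implies: assumed here, because SAP 6.5 has no such split.

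Formulas, with q = p × f and X ~ Binomial(n, q):
- Expected count = n × q.
- P(both zero) = (1 − q1)^n × (1 − q2)^n.
- P(worse bandage not higher) = 1 − Σ P(X1 = i) × P(X2 ≤ i − 1).
- Power = probability that an exact two-sided McNemar test gives p ≤ 0.05, with discordant probabilities q1(1 − q2) and q2(1 − q1).

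Example, 40% against 10% with f = 0.1: q1 = 0.04 and q2 = 0.01. Expected counts are 35 × 0.04 = 1.4 and 35 × 0.01 = 0.35. P(both zero) = 0.96^35 × 0.99^35 = 0.240 × 0.703 = 0.169.

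| Assumed rates | f | Expected counts | Both zero | Worse not higher | Power |
|---|---|---|---|---|---|
| 40% v 10% | 0.05 | 0.70 v 0.18 | 41.4% | 55.1% | – |
| 40% v 10% | 0.1 | 1.4 v 0.35 | 16.9% | 35.6% | 0.2% |
| 40% v 10% | 0.2 | 2.8 v 0.7 | 2.7% | 18.3% | – |
| 40% v 10% | 1 (all reported) | 14.0 v 3.5 | 0.0% | 0.2% | 77.0% |
| 50% v 20% | 0.1 | 1.75 v 0.7 | 8.2% | 36.9% | 0.4% |
| 50% v 20% | 1 | 17.5 v 7.0 | 0.0% | 0.5% | 67.6% |
| 30% v 10% | 0.1 | 1.05 v 0.35 | 24.2% | 46.5% | under 0.1% |
| 30% v 10% | 1 | 10.5 v 3.5 | 0.0% | 2.2% | 43.3% |

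With 30 subjects, 40% against 10% has power 68.1% when all reactions are reported and 0.1% at f = 0.1. Power serves here only as a measure of lost information; no test is proposed.

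As one concrete pattern, suppose 10 subjects had itching only at bandage A's site and 2 only at bandage B's. The exact paired p-value is 2 × (1 + 12 + 66)/4096 = 158/4096 = 0.039. That contrast would be visible only in data recorded and reported by site.

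**The case against.** Keeping expected procedural reactions out of the adverse event data is a stated and ordinary design choice in an exploratory study of marketed bandages. Exacerbated reactions are still captured. Redness and barrier function are analysed by product in Tables 14.2.1 and 14.2.2. All of this stands, and it narrows the gap to non-exacerbated bleeding, pain, itching and the like.

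Four stronger readings are tempting, but the documents do not support them.

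- A reader might infer that the safety tables would show zero against zero for bandages that differ. Under SAP 6.5 there is no split by bandage, so the tables as described make no bandage comparison at all.
- A reader might infer that the plan sets up an unsupported tolerability claim. None is planned: the objectives are microbiome, barrier function and redness, and SAP 6.2 calls all analyses exploratory.
- A reader might infer that unblinded staff decide what counts as exacerbated. Protocol 12.2 gives that judgement to the investigator. Protocol 10.7 includes personnel reviewing subject-reported events among those who cannot be reliably blinded, but it does not name the investigator and provides a code-break procedure.
- A reader might infer that a paired comparison with the uncovered wound is ready in data already collected. The case report form pages are not in the documents, and neither the visit procedures nor the legible schedule rows show a reaction check by site. The uncovered wound also cannot have bandage application or removal reactions, so that contrast is uneven for them.

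Two uncertainties remain. Some assessments are blacked out, so a redacted site assessment cannot be excluded, although none appears in the unredacted safety output. And if the case report form instruction were read as covering only exacerbated reactions, ordinary ones would be recorded nowhere, which would widen the gap.

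**Conclusion.** The point holds in this form: reactions that the protocol requires on the case report form appear in no planned output, and Protocol 14.4 and SAP 6.5 disagree on whether adverse events are shown by treatment. The safety section is therefore incomplete on local reactions other than redness and barrier change, and under the SAP text it cannot attribute even exacerbated reactions to a bandage.

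The size cannot be fixed from the documents. Over the assumed rates, with one reaction in ten exacerbated and 35 subjects, the worse bandage would fail to show the higher count 36% to 46% of the time even with a split by site, against 0.2% to 2.2% with full reporting. These figures rest on the assumed rates, the assumed exacerbation fraction and independence between sites. This is an inexpensive improvement to reporting and does not bear on the primary or secondary analyses.

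**What to change.** 1. Leave the adverse event definition unchanged.
2. Record the test-site number with each expected reaction on the case report form, if it is not already captured.
3. Add to SAP 6.5 and Appendix 1 one descriptive table on the safety set: number and percentage of subjects with each reaction type for each of the six site conditions, with an unassigned row for reactions that cannot be localised. Add a matching listing to Appendix 2.
4. Compare bandages with each other for application and removal reactions. Use the uncovered wound as reference only for stripping and healing reactions. Attach no tests.
5. Reconcile SAP 6.5 with Protocol 14.4 on presentation by treatment. If events are split by treatment, give those not tied to a site their own row.

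The cost is one table, one listing, possibly one case report form field, and slightly more data entry. The counts will be only as good as the consistency with which reactions are recorded, so the table should carry a note saying so.
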